**Number of target joints at end of study:**

Pre-existing target joints + new target joints – resolved target joints

**4.1.1.4 Frequency of Administration**

Baseline frequency of administration is reported in Previous Hemophilia Treatment for the past 6 months eCRF as ‘Previous Hemophilia Treatment during the stable SHL period’ and is converted to frequency per month.

The frequency of administration response is calculated over the entire intervention period:

- Intervention period (days) = (1 + Visit 6/EOS date – Visit 2 date)

The frequency of administration (/month) will be assessed using the record of prescribed dose regimen in the eCRF. These following are example calculations of the risk group planned dose frequency:

Example 1: Participant in high risk score group was prescribed 2x/week on Day 1 and remained in study until Day 182 (26 weeks) with no prescribed dose change. The total prescribed number of dose administrations is 26 weeks x 2/week. The frequency (/month) of prescribed Jivi prophylaxis is  $30.4375 \times$  total prescribed number of dose administrations/ dose interval (days) =  $[30.4375 \text{ (days/month)} \times 52] / 182 \text{ (days)} = 8.6964 \text{ / month}$ .

Example 2: Participant in low risk score group was prescribed 2x/week on Day 1, Q5D on Day 29, and Q7D on Day 57. The participant remained in study until Day 182 with no other prescribed dose change. The frequency of prescribed Jivi prophylaxis is  $30.4375 \text{ (days/month)} \times 32 \text{ total doses} / 182 \text{ (dose interval days)} = 5.3516 \text{ / month}$ .

- Frequency of administration (/month) =  $30.4375 \times$  total doses over intervention period of prescribed Jivi prophylaxis / Intervention period (days)
  - Frequency of administration will be rounded to 2 decimal digits.

Improved, similar, or worsening frequency of administration will be assessed by comparison of prescribed prophylaxis to the baseline frequency of administration (each expressed as infusions per month):

$$Infusions_{post} - Infusions_{pre} = \begin{cases} \geq 2 & \text{worsening} \\ (-2, 2) & \text{similar} \\ \leq -2 & \text{improved} \end{cases}$$

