#### Definitions

- No regimen change during study: participant is treated according to the score-assigned regimen and does not deviate or switch frequency.
- Improved ABR: Reduction from pre-study ABR is  $\geq 1$ .
- Similar ABR: Absolute change from pre-study ABR is  $< 1$ .

- Worse ABR: Increase from pre-study ABR is  $\geq 1$ .
- Decreased frequency of administration: Reduction from pre-study in number of infusions per month is  $\geq 2$ .
- Similar frequency of administration: Absolute change from pre-study in number of infusions per month  $< 2$ .
- Worse frequency of administration: Increase from pre-study in number of infusions per month is  $\geq 2$ .

Pre-study ABR and treatment frequency is based on data from a minimum of 6 continuous months (up to a maximum of 12 months) of stable SHL prophylaxis at any given time within the 12 months prior to screening. Stable SHL prophylaxis is defined as a minimum of 18 weeks of treatment in a 6 (consecutive) calendar month period in the 12 months prior to the screening visit.

A switch to a higher frequency regimen due to a bleed during study is considered as non-favorable outcome, whereas participants who switch due to other reasons (e.g. personal decision, study compliance issues, or changes in physical activity level) will be censored at time of switch.

The number (frequency) of participants switching the risk score-selected dosing regimen will be summarized.

As sensitivity analyses, the proportion of participants with favorable outcome on the risk score-selected prophylaxis regimen will be presented by inhibitor history.

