### 4.2.2 Main Analytical Approach

The analysis of the primary endpoint will be performed on the mITT population.

The entire study intervention period will be analyzed regardless of the score assigned dosing regimen (i.e. during the first 8 weeks on the study).

The strategy for primary endpoint analysis, including how to deal with participants who switch regimen frequency is listed below:

- A switch to a higher frequency regimen than the one assigned by the score, due to a bleed during study, is considered as non-favorable outcome
- Participants who switch due to other reasons than bleeding events (e.g. personal decision, study compliance issues, or changes in physical activity level) will be censored at the time of regimen change
  - switch after 4 months ( $> 122$  days): participant data will be analyzed until censoring
  - switch prior to 4 months ( $\leq 122$  days): participant data will not be used for analysis, as it is assumed that a shorter duration will not be sufficient to correctly estimate the ABR and would bias the results.

Note: a decrease in regimen per score assignment (during the first 8 weeks) is not considered a switch as discussed above.

Favorable outcome assessed by total ABR and frequency of administration (/month) is evaluated after considering regimen switch events.

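### Counting whole doses makes the frequency class depend on the exact end day for medium-risk participants from 2x/week whose follow-up ends early or whose Q5D start is late

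*SAP*

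**What the plan says.** SAP section 4.1.1.4 sets the on-study frequency at 30.4375 times "total doses over intervention period of prescribed Jivi prophylaxis / Intervention period (days". The denominator is "Intervention period (days) = (1 + Visit 6/EOS date – Visit 2 date". "Frequency of administration will be rounded to 2 decimal digits". The pre-study value "is converted to frequency per month", but no conversion factor is given.

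Two worked examples follow. In Example 1 (high risk, 182 days), "The total prescribed number of dose administrations is 26 weeks x 2/week", which gives 8.6964 per month. Example 2 reads "Participant in low risk score group was prescribed 2x/week on Day 1, Q5D on Day 29, and Q7D on Day 57" and uses 32 doses over 182 days, giving 5.3516. There is no medium-risk example, and no rule on whether a dose due on the final day counts.

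The protocol's definitions under section 9.4.2 set the cut-off: "Decreased frequency of administration: Reduction from pre-study in number of infusions per month is" at least 2. The SAP uses the same limit. Under SAP section 4.2.1, similar ABR with decreased frequency is favorable, while similar ABR with similar frequency is not.

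Participants with shortened follow-up stay in the analysis. The mITT set requires a minimum of 4 months. For those who switch regimen after Day 122 for reasons other than bleeding, SAP section 4.2.2 says "participant data will be analyzed until censoring".

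**The concern.** A class meant to describe a prescribed regimen should not change because follow-up stopped a day earlier or later. With a whole-number numerator and a day-count denominator, the computed rate falls a little each day and jumps up on each scheduled dose day. That is harmless far from the limits. Medium-risk participants from 2x/week are not far: going from 2x/week to Q5D after a first month on 2x/week reduces the monthly count by only slightly more than 2.

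At stake is the primary endpoint for such a participant when ABR is 'similar', because the frequency class then decides between favorable and non-favorable. The class also feeds the secondary table of improved, similar and worse frequency (SAP section 4.3.1), whatever the ABR.

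**Working it through.** **Plan's own figures.**
- Example 1: 30.4375 × 52/182 = 8.6964, as printed.
- Example 2: 8 doses (Days 1–28) + 6 Q5D doses (Days 29–54) + 18 Q7D doses (Days 57–176) = 32, and 30.4375 × 32/182 = 5.3516, as printed. Pro-rating would give 8 + 28/5 + 126/7 = 31.6 doses and 5.28, so the SAP does count whole doses.

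**Inputs for the medium-risk case.**
- Q5D from Day 29: the protocol synopsis says 4 weeks, and Example 2 switches on Day 29.
- Pre-study 2x/week = 30.4375 × 2/7 = 8.6964, or 8.70 rounded. This factor is an assumption.
- For censored participants, numerator and denominator are both taken to stop on the censoring day. This is also an assumption.

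**Whole-dose formula.** Doses to Day D, counting one due on Day D: 8 + floor((D − 29)/5) + 1. Rate = 30.4375 × doses/D, rounded to 2 decimals; change = rate − 8.70.

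| Day | Doses | Rate | Change | Class |
|---|---|---|---|---|
| 122 | 27 | 6.74 | −1.96 | similar |
| 123 | 27 | 6.68 | −2.02 | decreased |
| 124 | 28 | 6.87 | −1.83 | similar |
| 128 | 28 | 6.66 | −2.04 | decreased |
| 129 | 29 | 6.84 | −1.86 | similar |
| 154 | 34 | 6.72 | −1.98 | similar |
| 155 | 34 | 6.68 | −2.02 | decreased |
| 182 | 39 | 6.52 | −2.18 | decreased |
| 184 | 40 | 6.62 | −2.08 | decreased |

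**Why it stops.** On a dose day the whole count exceeds the pro-rated count by 0.8 dose. At Day 124 that is 0.8 × 30.4375/124 = 0.20 per month, against a pro-rated margin past the cut-off of 0.02. At Day 184 it is 0.13 against 0.21.

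**Count of 'similar' end days, Days 122–159 (38 days), Q5D from Day 29.**

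| Baseline | Last-day dose | 'Similar' days |
|---|---|---|
| 8.70 (rounded) | counted | 17; last is Day 154 |
| 8.6964 (unrounded) | counted | 19; last is Day 159 |
| 8.70 / 8.6964 | not counted | 10 / 11 |
| 8.67 (52/12 weeks per month) | counted | 23; flips run to Day 164 |
| 8.00 (4 weeks per month) | either | 38; never 'decreased', so no flip |

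**Planned completion, Q5D from Day 29.** Every end day from 180 to 197 is 'decreased' at baseline 8.70; the smallest reduction is 2.08, on Day 184.

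**Later Q5D start.** SAP Table 2 says 1 month, and the protocol's Appendix 7 makes the change at Visit 3, which the Schedule of Activities allows at Month 1 ± 7 days. At baseline 8.70:
- Start on Day 31 or 36, last-day dose counted: Days 181 (−1.97) and 186 (−1.99) are 'similar' and their neighbours 'decreased'. If that dose is not counted, no day from 180 to 197 is 'similar'.
- Start on Day 38, last-day dose counted: 'decreased' on Days 182, 187, 191, 192, 196 and 197, and 'similar' on the other 12 of the 18 days from 180 to 197.

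**Pro-rated formula.** For Q5D from Day 29, 30.4375 × (8 + (D − 28)/5)/D − 8.6964 gives −2.01 at Day 122, −2.12 at Day 150 and −2.21 at Day 182: one class throughout. For a Day 31 start it crosses −2 once, at about Day 129; for a Day 38 start once, at about Day 159.

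**The case against.** Four objections carry weight.

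- **Few participants.** It takes a medium risk score, prior 2x/week, an early end or late Q5D start, and 'similar' ABR; with improved ABR both classes are favorable. The documents give no expected number, the study is descriptive, and the planned confidence intervals are about 29 to 44 points wide at N = 20 to 25. This stands and keeps the point minor.
- **The end day is not wholly free.** Visit 6, which doubles as the early-withdrawal visit, should fall as close as possible to the next infusion. With Q5D from Day 29, visits aligned to dose days (124, 129 and so on) do not alternate. But up to Day 154 they are all 'similar' if the last-day dose counts and all 'decreased' if it does not, so the missing counting rule then decides the class. Censoring dates and unaligned withdrawals remain free to vary. Also, non-bleeding switchers at Day 122 or earlier are dropped, so Day 122 does not illustrate a censored switcher.
- **An existing sensitivity analysis.** SAP section 4.2.3 counts everyone who discontinued or switched as non-favorable, which takes the frequency class out of their result. It does not repair the main analysis, nor help a completer with a late Q5D start.
- **Any hard cut-off has a crossing.** True, but one crossing as follow-up lengthens differs from repeated reversals.

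A reader might infer that medium-risk participants from 2x/week are affected in general, or that pro-rating always returns 'decreased'. Neither is supported. On the Day 29 schedule six-month completers are stably 'decreased', and after pro-rating a delayed Q5D start still leaves one crossing.

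**Conclusion.** The point holds in a limited form. For medium-risk participants from 2x/week, the whole-dose formula makes the class alternate when follow-up ends at about Day 123 to 159 with Q5D from Day 29. When Q5D starts later, the alternation can extend into the planned Visit 6 window. It rests on a baseline of about 8.67 to 8.70 per month, which the SAP implies through Example 1 but does not state.

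The share of end days classed 'similar' is not a fixed property of the plan: it moves with the last-day-dose rule, the baseline conversion and the rounding. Each participant whose class is decided this way, with ABR 'similar', moves the primary proportion by 1/25 = 4 to 1/20 = 5 percentage points. It is a small but avoidable defect, and the correction is worth making because it is cheap.

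**What to change.** In SAP section 4.1.1.4:

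1. Replace the dose count with the sum, over prescribed regimens, of days on the regimen times its daily rate (2/7 for 2x/week, 1/5 for Q5D, 1/7 for Q7D, or one over the prescribed interval). Divide by total days and multiply by 30.4375.
2. Convert the pre-study weekly frequency with the same factor, 30.4375/7.
3. Compare unrounded values with −2 and +2; round only for display.
4. State that for censored participants both the regimen days and the denominator end at censoring.

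Example 1 stays at 8.6964 and Example 2 becomes 30.4375 × 31.6/182 = 5.28. A medium-risk example would help. This removes the repeated alternation and makes the last-day-dose question irrelevant.

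The 4-week and 1-month descriptions of the Q5D start should also be reconciled across the protocol and SAP; which of them applies is not a statistical question.

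The cost is one formula and one worked example in the SAP. No new data are needed, and no dose or clinical rule changes.

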**4.1.1.5 Incremental Recovery**

FVIII levels measured by a validated assay will be analyzed. Planned time points for assessment of incremental recovery are prior to start of infusion and 15 to 30 minutes after end of infusion.

Incremental recovery is calculated as shown below:

Incremental recovery =

(post-infusion FVIII level – pre-infusion FVIII level) \* weight (in kg)/ dose (in IU)

The most recent weight measurement will be used for calculation.

If a pre-infusion FVIII level value is below the lower limit of quantification (LLOQ), a data point with the value of one-half the LLOQ will be substituted.

A validity flag for incremental recovery values will be created. All incremental recoveries will be considered valid except when the following conditions apply:

- Pre-infusion FVIII >37.5% after 3 days, >23.1% after 4 days, >21.5 after 5 and 6 days, or >8.1% after 7 or more days
- Post-infusion FVIII value is below the LLOQ
- Post-infusion FVIII value is below Pre-infusion FVIII value

If an incremental recovery is flagged as not valid, then the corresponding pre-infusion, post-infusion and incremental recovery value will not be considered in tables displaying summary statistics of incremental recovery values and FVIII levels. FVIII levels that are not valid for calculation of incremental recovery will be listed.

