#### **8.4.7 Events of Special Interest**

Hypersensitivity reactions, including severe allergic reactions (which can progress to anaphylaxis), chest or throat tightness, dizziness, mild hypotension, and nausea, are known and listed adverse drug reactions for FVIII products and have been reported with use of Jivi. Loss of efficacy of the drug product has also been reported in children < 6 years of age and may be associated with the development of antibodies to PEG. Loss of efficacy can present as bleeding and must be confirmed by low recovery or post-infusion FVIII level, and a negative FVIII inhibitor test. A low recovery or no detectable FVIII post-infusion in a participant with a hypersensitivity reaction in the presence of PEG IgM antibodies is considered LoE even in the absence of a bleeding event. All such reported events (hypersensitivity and LoE) occurred early in treatment (within the first 4 EDs).

Hypersensitivity reactions and LoE are defined in this study as AESIs and must be reported within 24 hours of the investigator's awareness. The LoE must be confirmed by an abnormal low recovery after the infusion of Jivi.

In the event of reported LoE of the study intervention, the following is to be done:

1. Schedule a visit within 4 days of the reported event.
2. Obtain 2 pre-infusion blood/plasma samples for FVIII levels and FVIII inhibitor (for local laboratory).
3. Administer BAY 94-9027 (use current prophylaxis dose [IU/kg]).
4. Obtain one post-infusion blood/plasma samples (for local laboratory) for FVIII levels (15-30 minutes post-infusion).

Non-serious hypersensitivity events should not automatically be upgraded by the reporting investigator to serious.

If hypersensitivity reactions occur, immediately discontinue study intervention administration and initiate appropriate treatment. Please refer to the approved prescribing information.

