#### 4.4.3 Incremental Recovery and Trough Measurements of Jivi Levels

Actual sampling times before and after infusion and the dose administered will be presented in listings of FVIII levels. Incremental recovery FVIII levels will be presented with the corresponding participant weight value.

A summary of incremental recovery will be presented by risk group and also the frequency of samples failing validity criteria.

A summary of quantitative trough levels will be presented by risk group and also the frequency of trough levels above 1%, 3% and 5%.

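### Incremental recoveries with a post-infusion FVIII level below the LLOQ or below the pre-infusion level are left out of the recovery statistics without a documented error, so the summary can only shift upward

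*SAP*

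**What the plan says.** SAP 4.1.1.5 defines recovery as the post-infusion minus the pre-infusion FVIII level, multiplied by weight and divided by dose. Three conditions make a recovery not valid. One is a pre-infusion level above a limit that depends on the days since the last dose. The other two concern a low result after the infusion: "Post-infusion FVIII value is below the LLOQ" and "Post-infusion FVIII value is below Pre-infusion FVIII value". Neither of these asks for evidence of an error. The flagged pre-infusion, post-infusion and recovery values "will not be considered in tables displaying summary statistics of incremental recovery values and FVIII levels". The same section says that the levels concerned are listed.

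A low pre-infusion level is handled differently: "If a pre-infusion FVIII level value is below the lower limit of quantification (LLOQ), a data point with the value of one-half the LLOQ" is substituted and the sample stays in.

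SAP 4.4.3 promises the output: "A summary of incremental recovery will be presented by risk group and also the frequency of samples failing validity criteria". It does not say whether the failures are broken down by condition.

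Protocol 8.4.7 makes LoE an AESI and states: "The LoE must be confirmed by an abnormal low recovery after the infusion of Jivi". It also counts as LoE, even without a bleed, "A low recovery or no detectable FVIII post-infusion in a participant with a hypersensitivity reaction", provided PEG IgM antibodies are present. Otherwise a negative inhibitor test is needed as well. Protocol 8.3.1 reads a low post-infusion level without detectable inhibitors as probable loss of effect from anti-PEG antibodies.

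**The concern.** The protocol treats a very low post-infusion level as possible biology. The SAP treats the most extreme form of it as a measurement fault by definition. The recovery summary then describes only participants in whom the infusion produced a measurable level no lower than the one before it. The reported mean and minimum would look ordinary even if a participant had shown no recovery at all on Day 1. With 20 to 25 participants, and the summary given by risk group, one such participant matters to the description.

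The neighbouring rules point the other way. Pre-infusion values below the LLOQ are kept at half the LLOQ, and the trough rule in SAP 4.1.1.6 invalidates only high values. Recovery is the one place where a low result alone leads to exclusion.

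**Working it through.** The plan states no figure on this point, so there is none to reproduce. The check has five steps.

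**Inputs.** The validity conditions and recovery formula are from SAP 4.1.1.5, and the 20-25 expected participants from SAP section 5 and Protocol 9.2. The LLOQ, the typical recovery, the risk-group sizes and an LoE rate for ages 12 and over are not given. Where they are needed below, they are assumptions.

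**1. Direction.** Weight and dose are positive, so the sign of a recovery is the sign of post minus pre. Set any level below the LLOQ to half the LLOQ.
- Dropped, both levels below the LLOQ: recovery = 0.
- Dropped, post below the LLOQ and pre at or above it: recovery < 0.
- Dropped, post at or above the LLOQ but below pre: recovery < 0.
- Not dropped by these two conditions: post is at or above the LLOQ and not below pre, so recovery ≥ 0.

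Every value these two conditions remove is at or below zero, and every value they leave is at or above zero. Removal can raise the mean and minimum but cannot lower them.

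**2. One near-zero case.** Let n-1 recoveries equal r and one equal 0. The full mean is r(n-1)/n and the reported mean is r. The overstatement is n/(n-1) - 1 = 1/(n-1).
- n = 20: 1/19 = 5.3%
- n = 25: 1/24 = 4.2%
- illustrative risk group of 8: 1/7 = 14.3%
- illustrative risk group of 5: 1/4 = 25%

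The reported minimum moves from about 0 to r.

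**3. Two near-zero cases.** The overstatement is 2/(n-2): 2/18 = 11.1% at n = 20 and 2/23 = 8.7% at n = 25.

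**4. Chance that it arises.** For an assumed rate p, the chance of at least one case is 1 - (1-p)^n.

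| assumed p | n = 20 | n = 25 |
|---|---|---|
| 1% | 18% | 22% |
| 2% | 33% | 40% |
| 5% | 64% | 72% |

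These rates only show a range. Protocol 8.4.7 mentions LoE reports in children under 6, and Protocol 2.3 says primarily in that age group. Neither gives a rate for the study's ages.

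**5. The opposite error.** Suppose the pre- and post-infusion tubes of one participant are swapped and nobody documents it. A recovery of +r becomes -r, the mean becomes r(n-2)/n, and it is too low by 2/n: 10% at n = 20 and 8% at n = 25.

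**The case against.** The strongest reply is that LoE does not depend on this table. Under Protocol 8.4.7 the investigator reports it within 24 hours, schedules a visit within 4 days and takes new samples before and after an infusion. SAP 4.5.2 tabulates treatment-emergent AESIs from the AE form, whatever the recovery flag says. Flagged levels are listed and failures are counted. A reader might infer that the SAP deletes the evidence for LoE. The documents do not support that.

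Two other inferences also fail. The Day 1 recovery is not the only scheduled check: Protocol 8.5.1 adds a sample at least 4 hours after that infusion, a 72-hour level at Month 3 and a Month 6 trough, and low troughs stay in the analysis. Nor can it be said that the failure count pools a low post-infusion level with a high pre-infusion level. SAP 4.4.3 is silent, and the table shells are in a separate document.

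The rule also has a purpose. A level that falls 15 to 30 minutes after an infusion may well be a bad sample, and footnote g of the Schedule of Activities lets sites repeat levels that look wrong for the dose. Step 5 shows that a single undocumented swap would pull the mean down by about twice the upward bias from one dropped case. That is a sound argument against simply abolishing the flag.

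What stands is narrower. The AESI route works only if the investigator recognises the event. Footnote g directs a repeat at Month 3 without mentioning LoE, LoE can present as bleeding, and bleeds that are not serious are not recorded as AEs (Protocol 8.4.6). No reconciliation of flagged recoveries with AESI records is planned. None of the replies removes the one-sided effect on the summary itself.

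**Conclusion.** The point holds as a limited reporting defect. The two low post-infusion conditions exclude on the outcome, without a documented error, and can only raise the summarised recovery. One near-zero case means an overstatement of about 4-5% overall and more within a risk group. This assumes that such a case occurs and that the other recoveries are roughly equal.

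A low recovery that is above the LLOQ and not below the pre-infusion level stays in the statistics, so it would be wrong to say that the summary hides all poor recoveries. Recovery is not among the endpoints in Protocol section 3 or SAP 1.1. The study tests no hypothesis, and no primary or secondary result, regimen assignment or AESI count changes. The change is worth making because the summary would otherwise describe recovery only among those who recovered, and because it is cheap.

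**What to change.** In SAP 4.1.1.5 and 4.4.3:

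- Present the recovery summary twice, once with all samples and once without the flagged ones. In the all-samples version, set a post-infusion level below the LLOQ to half the LLOQ, as is already done before the infusion. Leave out a low post-infusion result there only for a documented sampling, timing or dosing error.
- Report validity failures by criterion, so that post-infusion below the LLOQ and post-infusion below pre-infusion are separate from a high pre-infusion level.
- Cross-list the low post-infusion failures with the LoE AESI records and any inhibitor results.

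The cost is a few sentences in the SAP, a second recovery summary, a split count and one listing. No new data are needed. The downside is that an undocumented swap lowers the all-samples mean, and that a participant with both levels below the LLOQ contributes exactly zero by construction. Showing both summaries lets the reader see how far the flagged samples move the result.
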